7.3 Statistical analyses

7.3.1 *Analysis of the primary endpoints*

7.3.1a Adaptive trial

The unit of analysis is at the patient-level. Therefore, for the primary outcome, we will use a generalized linear mixed model for binary outcomes to adjust for physician-level

clustering and multiple patient observations per physician. The study arms will be analyzed using a multivariable regression model, in which each of features of the EHR tools (“factors”) will be included as covariates in an overall regression model that compares the effect of receiving an enhanced EHR decision support tool compared with usual care. In specific, these factors will include: timing of EHR tool (open encounter=1, order entry=0), whether a follow-up alert is enabled as part of the tool (yes=1, no=0), cold state outreach is used (yes=1, no=0), simplification is used (yes=1, no=0), sign-off is used (yes=1, no=0), pre-commitment is used (yes=1, no=0) or if different risks of the high-risk medications are presented within the EHR tool (yes=1, no=0). In this way, we will also observe and report an overall effect of the enhanced EHR tool compared with usual care as well as the effect of individual features through their coefficients in the model. We will conduct this interim analysis once at the end of follow-up in Stage 1 to determine the arms with the most potential promise. In specific, the 15 active arms will be ranked based on their observed effect size at reducing prescribing of high-risk medications from the covariate coefficients from the models. At the end of follow-up in Stage 1, we will also use these regression models to explore whether any of the intervention arms (defined by factors) are inferior to usual care. We will repeat these analyses at the end of Stage 2 using all available data to determine whether any of the intervention factors (and secondarily, arms) were more effective than usual care at reducing prescribing of high-risk medications. In secondary analyses, we will include anticholinergics.

Because this is a randomized trial, our primary analyses are planned as unadjusted; in secondary analyses, we will adjust for patient age, race/ethnicity, and gender.. Given the nature of the data and how the outcomes are categorized, there will not be missing values for the primary endpoint, as the absence of action is classified as no action by the provider. For the primary analysis, we will include all eligible patients in the denominator who had at least one in-person or telehealth visit with their primary care provider. In secondary analyses, we will

include all eligible patients of those primary care providers in the denominator, regardless of whether the patient visited the provider over the follow-up period.

7.3.1b Replication trial

All analyses will use intention-to-treat principles. We will use generalized estimating equations to adjust for clustering and repeated observations. For the inappropriate prescribing outcome, we will use a log link function and binary distributed errors. For the adverse clinical outcomes, we will use a log link function and binary distributed errors. These models generate the estimated relative risks (RRs) with robust standard errors and are considered to be particularly appropriate when outcomes are common (e.g., incidences of $\geq 10\%$). Because this is a randomized trial, our primary analyses are planned as unadjusted; however, in secondary analyses, we will adjust for patient age, race/ethnicity, and gender.

Given the nature of the data and how the outcomes are categorized, there will not be missing values for the primary endpoint, as the absence of action is classified as no action by the provider. For the primary analysis, we will include all eligible patients in the denominator who had at least one visit with their primary care provider. In secondary analyses, we will include all eligible patients of those primary care providers in the denominator, regardless of whether the patient visited the provider over the follow-up period.

7.3.2 *Analysis of secondary endpoints*

For the secondary outcome of cumulative medication prescribing, will use an identity link function and normally distributed errors within the generalized linear models. For tertiary adverse clinical outcomes and resource utilization outcomes, we will use a log link function and binary distributed errors within the overall multivariable models. These models generate the estimated relative risks (RRs) with robust standard errors and are considered to be particularly appropriate when outcomes are common (e.g., incidences of $\geq 10\%$). For these outcomes from claims data, we will follow patients whose providers are randomized to the study from the time

of randomization until they are censored due to loss of continuous enrollment in their health plan or leaving Atrius Health. Due to the nature of the randomization, we do not anticipate any systematic differences in the amount of follow-up time per arm but will account for any imbalances using inverse probability censoring weights.

Because this is a randomized trial, our primary analyses are planned as unadjusted; however, if there are strong patient-level predictors of the outcomes not balanced by stratified randomization, we will adjust for these in the primary analyses. Given the nature of the data and how the outcomes are being measured, there should not be missing values. However, should there be sufficient missing data (e.g., >10%), we will use multiple imputation.³¹

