3.2.1 Stage 1 Design

In Stage 1 of the trial, we will randomize approximately 200 primary care providers at Atrius Health approximately equally to either usual care or active intervention. Of the half of providers randomized to active intervention, we will randomize them equally to one of 15 active intervention arms. Providers randomized to one of the 15 active intervention arms will receive an EHR tool to guide the care of their eligible patients. Providers randomized to usual care will receive no EHR tool, as is current clinical practice. Providers will be eligible for the trial if they prescribed a

benzodiazepine or sedative hypnotic to at least one older adult in the 180 days prior to randomization. We will randomize providers within strata based on their clinic size and baseline rates of high-risk medication prescribing.

Eligible patients of these providers will be who meet the following criteria: 1) older adults (aged 65 years or more) and 2) who have been prescribed at least 90 pills of benzodiazepine or sedative hypnotic in the last 180 days.

After 6 months (dictated by the average number of observed data points, i.e., at least 1 eligible patient for whom the EHR tools fired per physician), an interim analysis of Stage 1 participants will be performed to rank the 15 active intervention arms based on their observed effect size at reducing prescribing of high-risk medications. Up to 5 of the most promising active intervention arms based on their effect size will be tested in Stage 2. If more than 5 are promising, we will choose the top 5. If 1 to 5 arms are promising, we will choose those for testing in Stage 2. If none are promising, we will combine active interventions within the arms based on the most effective factors. After this interim analysis, the Stage 1 providers in the “winning” arms (i.e., the promising arms) will be randomly assigned to continue to receive their original treatment assignments or to usual care to test holdover/persistency effects. Similarly, the Stage 1 providers assigned to treatment arms determined to be statistically inferior will be randomly assigned in equal proportions to one of the winning arms or to usual care.

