3.2.2 Stage 2 Design

In Stage 2, we will randomize the primary care providers at Atrius Health who were assigned to usual care in Stage 1 in equal proportions to up to one of the 5 most promising treatment arms or to continue to receive usual care. We will also randomize any additional providers who prescribed at least one eligible anticholinergic to at least one older adult in the 180 days prior to randomization for secondary analyses. Providers randomized to one of the 5 selected treatment arms will receive an EHR tool to guide their care of eligible patients. As in Stage 1, we will randomize providers based on demographic characteristics, patient case-mix factors, and

baseline rates of high-risk medication prescribing. Patient eligibility will be identical to that used in Stage 1 except patients will also be included if they had been prescribed at least 90 pills of eligible anticholinergics in the last 180 days. Follow-up in Stage 2 will last at least 8 months, until enough data points have accrued.

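### If provider effects change between stages, the pooled final model as described gives standard errors that are too small; it needs a stage term and a provider-clustered variance

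*Combined protocol and SAP*

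**What the plan says.** Section 7.3.1a takes the patient as the unit of analysis. In one sentence split by a page break, it fits "a generalized linear mixed model for binary outcomes to adjust for physician-level" "clustering and multiple patient observations per physician". The covariates are the features of the tools. On other covariates it says that "our primary analyses are planned as unadjusted; in secondary analyses, we will adjust for patient age, race/ethnicity, and gender". It then states: "We will repeat these analyses at the end of Stage 2 using all available data".

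Between the two analyses the providers are allocated again:

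- Section 3.2.2 randomises the providers "who were assigned to usual care in Stage 1 in equal proportions" to one of up to five selected tools or to continued usual care.
- Under Section 3.2.1, Stage 1 providers in winning arms "will be randomly assigned to continue to receive their original treatment assignments or to usual care to test holdover/persistency effects".
- Under the same section, providers in the remaining tool arms are "randomly assigned in equal proportions to one of the winning arms or to usual care".

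For this model the plan names no stage term, no provider-by-stage effect, no between-stage correlation and no robust variance. Robust standard errors appear only for the replication trial (7.3.1b) and for the tertiary clinical and utilisation outcomes (7.3.2).

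**The concern.** Pooling the stages makes this a two-period cluster design in which many providers contribute patients under two different allocations. A single provider intercept treats two patients of one provider as equally correlated whether they belong to the same stage or to different stages. If a provider's own tendency to deprescribe shifts between stages for reasons unrelated to the tool, the model reads part of that shift as information about the tool. A fixed stage term removes only the average shift, and a logistic model has no free residual variance to absorb the rest.

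At stake is the final test of the adaptive trial's primary outcome: whether the tools, and their features, beat usual care. Section 3.2.3 carries two tools into the replication trial even if superiority is not shown. The exposure is therefore mainly in the confidence intervals and in any claim of effectiveness, and less in whether a replication takes place.

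**Working it through.** **The plan's own figure.** None is given for the standard error of the pooled model. The only related figure is the 80% power in Section 7.2, which names neither a comparison nor a number per arm. It could not be reproduced with the variants tried; that is a separate matter and does not decide this point.

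**How many providers switch.** Take 200 providers, half on usual care and half spread over 15 tools (3.2.1), and assume five winning arms, the maximum allowed.

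- Usual care to a tool: 100 × 5/6 = 83.
- Winning arm to usual care: 100 × 5/15 × 1/2 = 17.
- Losing arm to another allocation: 100 × 10/15 = 67.
- Total: 83 + 17 + 67 = 167 of 200.

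At the inputs below, a separate approximation puts about 78% of the information on the pooled tool contrast in within-provider change.

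**Inputs from the plan.** Event rate 5% and intra-provider correlation 0.3 (7.2). More than 2000 patients in Stage 1 and 4000 in Stage 2 (4.3.2), so 2000/200 = 10 and 4000/200 = 20 per provider. The Stage 2 count may include patients eligible only through an anticholinergic; 20 also equals the cluster size in 7.2.

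**Assumptions.** The correlation of 0.3 is on the latent logistic scale. The between-stage correlation ρ is varied. Event rates of 20% and 30% are shown as sensitivity cases.

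**Model.** For patient j of provider i in stage s:

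logit(p) = intercept + stage + tool terms + u_i + v_is

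- Total provider variance: σ² = 0.3/(1 − 0.3) × π²/3 = 1.41.
- Split: var(u) = ρσ² and var(v) = (1 − ρ)σ².
- Provider-specific change between stages: var(v_i2 − v_i1) = 2(1 − ρ)σ². At ρ = 0.8 this is 2 × 0.2 × 1.41 = 0.56. A single intercept sets it to zero.

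**Type I error of the tool test.** No true effect, Stage 2 allocation as in 3.2.1-3.2.2, random-intercept logistic model with a stage term, two-sided 5% test. The first two rows are from 800 simulated trials per setting, the last two from a second simulation with 500.

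| Event rate | ρ = 1 | 0.8 | 0.6 | 0.5 | 0.2 |
|---|---|---|---|---|---|
| 5% | 5.5% | 8.1% | 9.6% | – | – |
| 20% (assumed) | 5.0% | 11.1% | 16.3% | – | – |
| 5% | 5.4% | 7.8% | – | 12.0% | 15.0% |
| 30% (assumed) | 5.6% | 12.0% | – | 20.2% | – |

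Monte Carlo error with 800 trials is √(0.055 × 0.945/800) = 0.8 points at 5.5% and √(0.163 × 0.837/800) = 1.3 points at 16.3%.

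**Standard errors.** In the second simulation at 5% events, mean model-based SE divided by empirical SE for the tool effect was 0.94, 0.88, 0.79 and 0.74 at ρ = 1, 0.8, 0.5 and 0.2. The simulation error of these ratios is about 1/√(2 × 500) = 3%. Part of the shortfall (1 − 0.94 = 6%) is therefore seen even without drift.

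**Two checks on the cause and the remedy.**

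- With Stage 2 data alone, so one period per provider, type I error without a secular trend stayed between 4.2% and 6.6% at every ρ. The problem lies in the pooling.
- With a provider-clustered sandwich variance on the pooled data, it stayed at about 5%-6% throughout the 800-trial settings.

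**Stage term.** Without one, an assumed secular trend of 0.4 in log odds shifted the estimated tool effect by 0.11-0.12 log odds and gave type I error of 15%-19%. Under five winning arms more than half of providers hold a tool in Stage 2, against half in Stage 1, so stage and tool are associated.

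**Limits.** Equal cluster sizes; winning arms chosen at random, so no selection effect; no sandwich results to hand for single tool features.

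**The case against.** **The structure is inferred.** The plan never writes out the random effects. A single provider intercept is the natural reading but not a stated one, and the sponsor may intend a richer structure. This stands. It leaves the text permitting the version that fails under drift, so the plan still has to say which is meant.

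**The harm is conditional.** A reader might infer that the standard errors are wrong in any case and that the 5% test is certainly not a 5% test. The documents do not support that. At ρ = 1 the error rate is near nominal, and no between-stage correlation is given. The planned test of holdover does not settle it either, because holdover is carry-over of treatment and not random drift of individual providers. What can be said is that exact stability is an unstated assumption. The stages also differ in length (6 months against at least 8), and one component of the outcome, the absence of any order in the window, depends on that length.

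**The size at the plan's inputs is modest.** At 5% events and ρ = 0.8 the rate is about 8%, and for the timing feature 6.6% against 6.2% at ρ = 1. A linear approximation gives slightly lower values for the tool, about 6.5% at 0.8 and 8% at 0.6. Rates of 16% to 20% rest on event rates that the plan does not state. All of this stands.

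**Scope.** A reader might extend the point to every secondary outcome. Section 6.2 defines the secondary and tertiary outcomes for Stage 2 and the replication trial, so only analyses of the primary outcome are pooled in this way. Nor do all providers change arm: some keep usual care or their winning tool, and with a single winning arm only half of the usual-care group would switch.

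**Conclusion.** The point holds in conditional form. As naturally read, the pooled end-of-Stage-2 model is anti-conservative for the tool effect whenever provider effects are less than perfectly correlated between stages. At the plan's 5% event rate the two-sided error rate rises from about 5%-6% to about 8% at correlation 0.8 and 10% at 0.6. At an assumed 20% event rate it rises to about 11% and 16%.

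These figures rest on an assumed between-stage correlation, on reading the 0.3 as latent-scale, on five winning arms and on a stage term that the plan does not name. It is worth changing because the remedy is cheap and performs well whether or not there is drift. It ranks below a must-fix because the documents do not show that drift exists or how large it is.

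**What to change.** In 7.3.1a, for the pooled end-of-Stage-2 analysis of the primary outcome and for secondary analyses of that outcome, add one line: the model includes a fixed effect for stage, and standard errors come from a sandwich estimator clustered on provider across both stages. Clustering on provider also covers patients who contribute to both stages under the same provider.

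A provider-by-stage random intercept is a possible alternative but may be poorly estimated here: at 5% events and 10 patients, each provider has 10 × 0.05 = 0.5 expected events in Stage 1. Its error rate has not been properly tested (only a pilot of 16 runs), so it should not be treated as equivalent to the sandwich. If the sponsor means the final analysis to use Stage 2 data only, the plan should say so.

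The cost is one line in the plan. Intervals widen if provider effects drift and stay about the same if they do not. The choice should be fixed before the pooled data are analysed.

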7.1 Statistical Hypotheses

Our null hypothesis will be that rates of provider prescribing (defined by evidence of a reduction in prescribing of high-risk medication) in any one of the intervention groups (defined by factors) will be no different than in the other arms, including the usual care arm.

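### The final adaptive-trial model, read as pooling both stages, has no stage term, so a rate difference between stages would bias the factor and tool effects; the seven factor tests also lack a multiplicity rule

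*Combined protocol and SAP*

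**What the plan says.** Section 7.3.1a models the binary outcome with a provider-level random effect and seven indicators: timing, follow-up booster, cold state outreach, simplification, sign-off, pre-commitment and risk framing. After Stage 1 the model ranks the arms. For the final analysis the text is "We will repeat these analyses at the end of Stage 2 using all available data", and the aim is "to determine whether any of the intervention factors (and secondarily, arms) were more effective than usual care". On covariates it says: "Because this is a randomized trial, our primary analyses are planned as unadjusted". The secondary adjustment there is for age, race/ethnicity and gender, and section 7.3.5 adds provider, patient and practice characteristics. Stage appears in neither list.

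The design changes between stages. In Stage 1 about half of the providers are on usual care and the rest are spread over 15 arms. In Stage 2 the Stage 1 usual-care providers are split equally over up to five kept arms and usual care (section 3.2.2). Providers in winning arms "will be randomly assigned to continue to receive their original treatment assignments or to usual care to test holdover/persistency effects", and those in arms found inferior "will be randomly assigned in equal proportions to one of the winning arms or to usual care" (section 3.2.1). The interim analysis comes "After 6 months (dictated by the average number of observed data points"; for the second stage, "Follow-up in Stage 2 will last at least 8 months, until enough data points have accrued".

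The null hypothesis in section 7.1 is that the outcome rate "in any one of the intervention groups (defined by factors) will be no different than in the other arms". Section 7.2 names a Holm-Bonferroni correction for the replication trial only.

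**The concern.** Randomization protects comparisons within each stage. It does not protect a pooled comparison when the allocation ratio differs between stages, because arm and stage are then associated by design. The provider effect does not remove the association, since providers change arm exactly at the stage boundary.

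Different stage rates are plausible, in either direction. Under section 6.2 a patient counts as a success for a taper at any time in the window, so a longer window can only raise that component. The component for no order during follow-up can only fall as the window lengthens. Active discontinuation without a later order can move either way. The 180-day pill criterion is applied again in Stage 2, so patients who stopped early in Stage 1 would tend not to requalify.

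At stake are the adaptive trial's own conclusions. A difference between periods could be reported as the effect of a behavioural feature or of the tools, or could mask one. Separately, a null that covers any factor-defined group, tested seven times without a rule, leaves unclear what counts as a positive result.

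**Working it through.** **Planned effect.** Section 7.2 assumes a 5% rate and an odds ratio of 1.15. Odds: 0.05/0.95 × 1.15 = 0.0605; rate: 0.0605/1.0605 = 5.71%, so +0.71 points against usual care. The documents give no stage-specific rate to reproduce.

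**Is pooling the right reading?** With five arms kept, Stage 2 has six groups and hence six means. The model needs an intercept, an overall enhanced-tool effect and seven factors, nine parameters in all. A rank check over all possible kept sets shows that Stage 2 alone identifies on average 1.9 of the seven factor coefficients (at most 4), and 0.2 with two arms. Stage 2 data alone could not answer the stated question.

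**How far the arm mix shifts.** Assumptions: 210 providers for whole cells (105 usual care, 15 × 7; the documents say about 200), five arms kept, winners split 1:1, and all ten non-kept arms re-randomized, either equally over six groups or 50:50 between usual care and the kept arms.

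| | Stage 1 | Stage 2, equal split | Stage 2, 50:50 |
|---|---|---|---|
| Usual care | 105 | 17.5 + 17.5 + 11.7 = 46.7 | 17.5 + 17.5 + 35 = 70 |
| Kept arms | 35 | 87.5 + 17.5 + 58.3 = 163.3 | 87.5 + 17.5 + 35 = 140 |
| Dropped arms | 70 | 0 | 0 |

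Stage 2 supplies 163.3/198.3 = 82% or 140/175 = 80% of kept-arm provider-periods, none of the dropped-arm ones, and 46.7/151.7 = 31% or 70/175 = 40% of the usual-care ones.

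**Crude bias.** With no true effect, shift = (Stage 2 share of tool data − Stage 2 share of usual-care data) × stage difference. With equal patients per stage this is 163.3/268.3 − 46.7/151.7 = 0.30, or 140/245 − 70/175 = 0.17, points per 1-point difference.

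**Linear model with provider correlation.** Generalized least squares, correlation 0.1 and 0.3, with 20 patients per provider in both stages (section 7.2) or 10 then 20 (section 4.3.2: 2000 and 4000 patients over about 200 providers). Shift per 1-point stage difference, five arms kept:

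| Estimate | No stage term | Stage term |
|---|---|---|
| Any tool v usual care | 0.22 to 0.48 | 0 |
| Kept feature | about +0.35 to +0.67, depending on how arms are selected | 0 |
| Dropped feature | about −0.5 to −0.65 | 0 |
| Timing (absolute) | about 0.25 to 0.3 | 0 |

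The first row exceeds the crude figure because the model weights within-provider changes, which occur at the stage boundary. It refers to a single tool-versus-usual-care contrast, not to the enhanced-tool coefficient held alongside the factors. That contrast shifts by 0.12 to 0.29 with two arms kept and by 0 with one.

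**Mixed logistic model.** No true effect, five arms ranked on Stage 1, latent correlation 0.3, 400 runs per scenario. Stage 1 rate 5%; the Stage 2 rates are assumptions. Paired figures are for 10/20 and 20/20 patients.

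| Stage 2 rate | Overall OR, no stage term | Any of seven factors p<0.05: without v with the term |
|---|---|---|
| 4% | 0.92 / 0.92 | 5% v 17% / 10% v 24% |
| 5% | 1.01 / 1.01 | 8% v 15% / 19% v 24% |
| 5.5% | 1.06 / 1.05 | 17% v 17% / 28% v 26% |

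With the term the overall OR is 1.00 to 1.02.

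**Multiplicity.** Seven independent tests at 0.05: 1 − 0.95^7 = 30.2%. Under the design's correlations, with arms kept independently of the data, about 23 to 28%. Holm's first step is 0.05/7 = 0.0071.

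**The case against.** The strongest objection is that the bias is conditional. The documents give one rate, the two clear effects of a longer window oppose each other, and with equal rates nothing is lost by omitting the term. That stands, and the point claims no more. A reader might infer that 8 months instead of 6 must raise the rate, for instance by a constant-hazard scaling of 5%. That does not fit an outcome that includes no order during follow-up.

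A reader might also set kept against dropped features and quote the combined shift. Section 7.3.1a reads each feature through its own coefficient and tests no such contrast. Nor is a feature's coefficient directly comparable with the planned effect, which is against usual care; only the overall tool effect is.

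The stage term is not justified by error rates: in the table above, the chance of any significant factor is higher with the term at 4% and 5% and about equal at 5.5%. The term also worsens holdover dilution. With five arms kept, 62.5 to 75% of Stage 2 usual-care providers had a tool before (29.2/46.7 and 52.5/70). If all of them kept the full effect, the overall estimate would fall by 23 to 39% as planned and by 34 to 46% with the term. Both objections stand and shape the fix.

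On the text, pooling is inferred, and the word unadjusted is set against demographic covariates, so it does not expressly exclude a design term. The gap is one of silence. The provider shares also rest on re-randomizing every non-kept arm, whereas section 3.2.1 speaks of arms found statistically inferior. The branch in which no arm is promising and interventions are combined was not modelled.

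**Conclusion.** The concern holds as a conditional bias. On the natural reading, the final model pools two stages with different arm mixes and no stage term. Per 1-point stage difference the overall tool effect moves by about 0.2 to 0.5 points, or 31 to 68% of the planned 0.71 (0.22/0.71 and 0.48/0.71), and the feature coefficients move as tabulated. This assumes five arms kept, winners split 1:1 and all non-kept arms re-randomized. Fewer kept arms reduce the overall shift.

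A reader might conclude that the final analysis is biased, or that the replication trial is put at risk. The documents support neither. No rate difference is documented, two arms go forward to replication in any case, and a shift common to the kept arms largely leaves their ranking alone.

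The multiplicity gap is secondary and applies whether or not the stages are pooled.

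**What to change.** 1. State in section 7.3.1a that both stages are pooled, and add a fixed effect for stage to the final primary model. Cost: one term; overall standard error 0 to 8% larger (log OR 0.145 to 0.157 at 10/20 patients, 0.123 to 0.130 at 20/20); single factors 2 to 3% larger on average, up to 18% in the worst case.
2. Apply Holm across the seven factor tests, in line with the replication trial. Cost: some power.
3. As a sensitivity analysis only, report the same model with a prior-exposure term for usual-care providers who had a tool in Stage 1, because the stage term alone increases holdover dilution. State its precision cost: overall standard error 34 to 77% larger in the linear check, 37 to 59% in the mixed model.
4. Report pooled estimates for kept arms and features with a caution that reusing the selection data inflates them. With no true effect and the stage term fitted, kept features still average an odds ratio of 1.16 to 1.26, against 1.01 when arms are picked at random. Neither the stage term nor Holm corrects this.

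Replacing the arm comparisons with tests on Stage 2 data alone is not recommended. It departs from the plan's use of all available data and costs about 1.2 to 1.3 times the standard error even with adjustment for each provider's Stage 1 rate. Trial conduct and data collection are unchanged.
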